Post-Treatment Session and 3-Month and 6-Month Follow-Up. To eliminate the burden of travelling to study appointments for assessments, telephone surveys will be conducted at the end of the mCM/mobile assessment phase. At that phone visit, participants will complete measures (read aloud by study coordinator) about treatment acceptability, smoking, medication adherence, self-efficacy to quit/remain quit, and physical activity.

Participants will be contacted by phone at 3- and 6-months post-screening visit. During the phone visit, participants will complete measures (read aloud by study coordinator) about smoking, medication adherence, self-efficacy to quit/remain quit, and physical activity. If participants report smoking abstinence at the 3 and 6-month follow-ups, they will be asked to come to the laboratory to provide a saliva sample and CO reading to bioverify smoking abstinence. If any participant is unable to come to the laboratory, he/she will be asked to provide a saliva sample by mail. When saliva is collected by mail, participants are sent instructions, saliva vials, a brief tobacco use assessment (that includes use of nicotine replacement therapies in the prior week), and a postage-paid padded envelope for returning the sample to the study coordinator. At each time point, any participant who provides a saliva sample will be paid \$50. All sample identification will be with an assigned study number rather than patient identifiers. Saliva samples will be mailed to Salimetrics, LLC for cotinine assay (see "Smoking-Cessation Outcome Measures and Biochemical Verification" herein).

Participant Reimbursement. Participants who drop out will receive partial reimbursement for the time and effort they devote to the study. Because monetary reinforcement is an essential part of the intervention we are studying, participants will receive payments as reinforcers during treatment in addition to payments they receive to compensate for their time and effort on the study. Participants are paid: 1) \$100 for completion of the screening visit and mCM training; 2) up to \$798 for mCM; 3) \$50 for equipment return at the end of treatment; 4) \$25 each for the assessments at 3- and 6-month follow-up; and 5) \$50 (each) for provision of saliva samples at 3- and 6-month follow-up. Participants could be paid up to \$1098 for their complete participation.

Study Measures

Table 2 outlines measures to be given at each time point in the study.

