Smoking-Cessation Outcome Measures and Biochemical Verification. Our choice of primary and secondary smoking endpoints follows recommendations by the Society of Research on Nicotine and Tobacco (SRNT; Hughes et al., 2003). Self-reported and bio-verified prolonged abstinence at the 3- and 6-month follow-ups will be the primary endpoints. Prolonged abstinence will exclude tobacco use in the first 2 weeks following the quit date (Hughes et al., 2003). Self-reported prolonged abstinence will be verified by cotinine assay. CO and saliva samples will be collected from participants who report prolonged abstinence at each follow-up. Saliva samples will be sent to the Duke University Nicotine Research Program to be analyzed for the presence of cotinine using a standard cut point of 10 ng/ml to determine abstinence. A blind sample of 5% will be rerun to assure test accuracy of saliva samples. Secondary smoking outcomes will include 7- and 30-day point prevalence abstinence at each assessment, where abstinence is defined as no tobacco use in the prior 7 or 30 days respectively. Additionally, participants will be asked if they have made one or more quit attempts in each follow-up period using a time-line follow back method (Lewis-Esquerre et al., 2005). We have recent experience using this method to assess daily smoking behavior (Carpenter et al., 2015).

Potential Risks

There is a risk of discomfort or distress in answering questions on the study measures. However, distress and discomfort related to questionnaire completion is usually temporary and well-tolerated. Risks also include discomfort related to quitting smoking. Quitting smoking may cause difficulty concentrating, poor sleep, increased appetite, anxious or depressed mood, and craving for cigarettes. Participants will be offered NRT, and there are risks associated with the use of NRT. Minimal risks associated with wearing a nicotine patch include skin irritation, dizziness, lightheadedness, increased heart rate or blood pressure, nausea or vomiting. If a participant indicates a contraindication to NRT (e.g. uncontrolled hypertension), medical clearance for NRT will be sought from the participant's primary care physician and/or the study physician. If a participant with a seizure disorder, history of or current hepatitis and/or cirrhosis, renal

impairment, and/or uncontrolled diabetes wishes to enroll in the study, he/she will not receive contraindicated medications.

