Self-reported and bioverified prolonged abstinence from smoking at the 3 and 6-month follow-up will be the primary end-point. Prolonged abstinence will exclude tobacco use in the first two weeks following the quit date to give participants time to achieve initial abstinence (Hughes et al., 2003). Self-reported prolonged abstinence will be verified by cotinine assay, a metabolite of nicotine in the saliva. Saliva samples will be collected from participants who report prolonged abstinence at each follow-up. They will be mailed to Salimetrics LLC for saliva cotinine assays. Saliva samples will be analyzed for the presence of cotinine using a standard cut point of 10 ng/ml to determine abstinence. A blind sample of 5% will be run again to assure test accuracy of saliva samples. Secondary smoking outcomes will include 7- and 30-day point prevalence abstinence at each assessment, where abstinence is defined as no tobacco use in the prior 7 or 30 days, respectively.

Data Analyses

Descriptive statistics will be used to summarize all study variables, including smoking history and current use, nicotine-dependence level, self-efficacy, readiness to change, and social support. For continuous variables, means, standard deviations, ranges, and histograms will be generated. For categorical variables, frequencies and proportions will be generated. Individual and mean trajectory plots of the longitudinal outcome variables will be constructed to understand their general trends over time (i.e., post-treatment, 3- and 6-month follow-ups). We will examine all variables to determine if parametric distributional assumptions (e.g., normality for the continuous variables) are valid. Variables not meeting distributional assumptions will either be transformed or modeled using non-parametric or semi-parametric methods (e.g., quasi-likelihood methods; McCullagh & Nelder, 1989). In order to describe the compliance/completion of the sample in terms of smoking-cessation aids and intervention completion, these variables will be summarized. In terms of descriptors for outcome measures, we will record number of quit attempts, quality of life, and number of weekly steps, and utilize time-line follow-back data to identify when participants may have lapsed. Potential covariates (e.g., age, gender, minority status) will be evaluated for inclusion in models. If any of these variables have a significant bivariate effect on treatment outcomes, they will be entered first in statistical models.

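### Bioverified abstinence is decided by saliva cotinine at 10 ng/ml with no exception for trial-supplied NRT and no decision role for the follow-up CO reading, so an abstainer still on NRT can be counted as not abstinent

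*Combined protocol and SAP*

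**What the plan says.** The section *Outcome Measurement and Biochemical Verification* defines the endpoint: "Self-reported and bioverified prolonged abstinence from smoking at the 3 and 6-month follow-up will be the primary end-point". It gives the method, "Self-reported prolonged abstinence will be verified by cotinine assay, a metabolite of nicotine in the saliva", and the decision rule, "Saliva samples will be analyzed for the presence of cotinine using a standard cut point of 10 ng/ml to determine abstinence". The earlier section *Smoking-Cessation Outcome Measures and Biochemical Verification* names the same assay and the same cut point. Neither section mentions NRT.

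CO appears in two places. The earlier outcome section says "CO and saliva samples will be collected from participants who report prolonged abstinence at each follow-up". *Post-Treatment Session and 3-Month and 6-Month Follow-Up* asks participants who report abstinence to come to the laboratory "to provide a saliva sample and CO reading to bioverify smoking abstinence". No follow-up CO cut point is given, and nothing says how CO and cotinine combine. For those who cannot attend, "If any participant is unable to come to the laboratory, he/she will be asked to provide a saliva sample by mail"; no CO reading is mentioned for this route.

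NRT is part of treatment. *Pharmacotherapy for Smoking Cessation* provides a patch plus an 8-week course of gum or lozenge to medically eligible participants, and Table 1 starts NRT at the quit date (Session 4). NRT use is also recorded. The form sent with mailed saliva kits asks about the prior week, and Table 2 lists use of cessation aids at 3 and 6 months without a look-back period.

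**The concern.** The endpoint is about smoking, but the marker responds to nicotine from any source, and the trial itself supplies nicotine. The protocol's own description of cotinine is enough to show the mismatch. A participant who has stopped smoking and still uses NRT can exceed 10 ng/ml and fail verification.

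The data needed to recognise such a participant are largely planned, but they have no part in the classification. Suppose someone reports abstinence and NRT use, has a low CO reading and has cotinine above the cut. The follow-up section suggests that CO helps to verify this person; the two outcome sections count the person as a failure. Two analysts could report different primary results, and the choice would be made after the data were seen.

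Efficacy is one of the pilot's three stated purposes, and *Data Analyses* says the data are to inform a larger RCT. Both the estimate and the rule could carry forward.

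**Working it through.** The plan has no figure of its own on this point. Two things can be worked out: whether supplied NRT can still be in use at the follow-up visits, and what one misclassification does to the rate.

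**Inputs**
- Table 1: Session 1 to Session 2 takes 1, 2 or 3 weeks; 1 week more to Session 3; 1 week more to Session 4, the quit date and start of NRT.
- *Pharmacotherapy for Smoking Cessation*: 8-week course (56 days) of gum or lozenge. Whether the 8 weeks also cover the patch is not clear.
- Table 1: follow-ups fall 3 and 6 months after Session 1, which is 89–92 and 181–184 days in calendar months.
- *Participants*: 15 enrolled, 10 completers.
- Assumption: gum or lozenge starts with the other NRT at the quit date.

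**Timing**, with Session 1 as day 0

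Quit day = 7 × (first interval in weeks + 1 + 1). Course end = quit day + 56. Gap = visit day − course end.

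| First interval | Quit day | Course end | Gap to 3 months (days) | Gap to 6 months (days) |
|---|---|---|---|---|
| 1 week | 21 | 77 | 12 to 15 | 104 to 107 |
| 2 weeks | 28 | 84 | 5 to 8 | 97 to 100 |
| 3 weeks | 35 | 91 | −2 to 1 | 90 to 93 |

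A negative gap means that the course is still running at the visit. If the quit day is counted as the first day of the course, each gap grows by one day. The saliva sample follows the phone visit by an unstated delay, which would also lengthen the gap.

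On-schedule gum or lozenge use therefore reaches the 3-month visit only with the longest first interval. Late or slow use, or a patch course longer than 8 weeks, would widen the overlap. At 6 months only use well beyond the course matters.

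**Effect of misclassification**

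The fall in the verified rate is k/n for k abstainers misclassified among n, whatever the true rate.

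| Cases (k) | n = 15 | n = 10 |
|---|---|---|
| 1 | 6.7 points | 10 points |
| 2 | 13.3 points | 20 points |
| 3 | 20.0 points | 30 points |

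These rows are illustrative. The documents do not say how many abstainers will be on NRT at follow-up, and k cannot exceed that number.

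**Could another part of the plan supply the missing rule?** The CO criteria in *Mobile CM Procedures* (below 6 ppm, and in the first week a proportion of the baseline reading) govern incentive payments during treatment. Nothing extends them to the follow-up endpoint. The recorded NRT use is not linked to classification anywhere.

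**The case against.** The strongest reply is that exposure is small. For two of the three first intervals an on-schedule course is over at least 5 days before the 3-month visit, and at 6 months it has been over for about three months or more. The paragraph on medication adherence attaches bupropion to the 3- and 6-month recording of medication days, and only bupropion is said to continue to 6 months. One reading is that the plan does not expect NRT use at follow-up. The documents also give no cotinine level for gum, lozenge or patch, so they cannot show that a given user would exceed 10 ng/ml. CO is collected expressly for bioverification, so the fault could be called an incomplete rule rather than a wrong one. The pilot is small and descriptive, and its 7- and 30-day secondary outcomes are defined as no tobacco use, without reference to the cotinine cut.

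Most of this stands as a limit on size. It does not remove the fault. The mailed-kit question and the cessation-aids item at 3 and 6 months show that NRT use at follow-up was thought possible. A reading with no cut point cannot overturn a cotinine result, so the rule that can actually be applied is cotinine alone. That rule can misclassify a true abstainer, which is more than a missing detail.

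**Conclusion.** The concern holds. As written, the primary endpoint is decided by a nicotine marker in a trial that supplies nicotine, with no exception for NRT users and no usable role for CO. For affected participants the error goes one way, towards a lower verified rate. It is more likely at 3 months than at 6.

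The number affected is unknown and may be zero; each case costs 6.7 points (n = 15) or 10 points (n = 10). This rests on NRT starting at the quit date, on calendar months counted from Session 1, and on some abstainers using enough NRT near the visit to exceed the cut. The rule should be corrected before follow-up results are classified. It does not undermine the pilot as a whole, because the results are descriptive and the secondary outcomes are not stated to depend on the cotinine cut.

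**What to change.** Put one rule, in the same words, in both outcome sections:

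1. Record nicotine-product use in the prior 7 days with every sample, through the existing cessation-aids item where it covers this.
2. Verify participants who report no NRT by cotinine at 10 ng/ml.
3. Verify participants who report NRT by the CO reading already planned at the laboratory visit, with a follow-up CO cut point fixed in advance. The 6 ppm payment threshold would have to be adopted explicitly if it is the one meant.
4. Report mailed samples above the cotinine cut from NRT users as unverified, and show the primary result with them counted as abstinent and as not abstinent.
5. Give the number verified by each route.

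The cost is one rewritten paragraph used twice and, at most, a look-back period added to an existing item. No visit or assay is added. The drawback is that CO detects only recent smoking, so verification of NRT users is less sensitive and some false positives may replace false negatives. The counts by route let a reader see how far the result depends on CO.

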In light of recent advances in the development of mobile interventions for exercise (Fanning, Mullen, & McAuley, 2012) and evidence that treating physical inactivity concurrently with smoking may increase short-term abstinence above and beyond typical smoking interventions (Spring et al., 2009), we have designed a Smoking Treatment and Exercise Program for Underserved Populations (STEP UP) that uses mobile CM (mCM) to simultaneously promote smoking cessation and physical activity.

The purpose of this pilot project is to evaluate the feasibility, acceptability, and efficacy of STEP UP. Given the heightened prevalence of smoking and physical inactivity among low-income populations, in addition to structural barriers to treatment, we propose to target low-income smokers with this intervention.

Methods

Participants

Participants will be adult men and women who smoke cigarettes. We plan to enroll 15 participants in order to reach a goal of 10 study completers.

Participants will be eligible for inclusion in the study if they meet the following criteria:

- current household income less than twice the federal poverty guidelines (Finer & Henshaw, 2006; for instance, someone from a family of 4 must have a household income less than \$48,500 to be eligible)
- currently smoke >10 cigarettes a day
- smoking for at least the past year
- can speak and write fluent conversational English
- are 18-70 years of age
- are willing to make an attempt to quit smoking and increase physical activity

Participants will be excluded from the study for the following:

- inability to walk
- expected to have unstable medication regimen during the study
- currently receiving non-study behavioral treatment for smoking
- myocardial infarction in the past 6 months
- contraindication to nicotine replacement therapy (NRT) or bupropion with no medical clearance
- exclusive use of other forms of nicotine such as cigars, pipes, e-cigarettes, or chewing tobacco
- current pregnancy

- current imprisonment or psychiatric hospitalization

Recruitment

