2 weeks post-mCM treatment follow-up			
8	Phone	Questionnaires; equipment return; treatment adherence measures	\$50 for equipment return
3 months after Session 1			
9	Phone/Lab	Questionnaires; return to lab and provide a saliva sample if abstinence reported	\$25 for assessment; \$50 for saliva sample
6 months after Session 1			
10	Phone/Lab	Questionnaires; return to lab and provide a saliva sample if abstinence reported	\$25 for assessment; \$50 for saliva sample
TOTAL COMPENSATION POSSIBLE			\$1098

Once a participant reports to the laboratory to begin the study, the study staff member obtaining consent will explain the study in detail, provide the participant with an IRB-approved written consent form explaining the procedures and risks, and answer any questions. The initial consent process and documentation takes place in a quiet, private office at DUMC (Hock Plaza space), and participants are given the chance to thoroughly read the consent prior to participation. Participants are given a copy of the signed informed consent form, and are given phone numbers to call if they have additional questions about the consent form or the research, if they have any problems during the study, or if they have questions about participating in research studies in general. No study procedures will begin until informed consent has been obtained.

After providing informed consent, potential participants will provide a breath sample to assess CO level, and will complete measures (see Measures section herein) regarding mood, exercise and smoking history, and sociodemographic data. Urine samples will also be used to screen for illicit drug use (to document use). Because the study drugs are each Category C drugs, urine pregnancy tests will also be completed for women of childbearing potential. We have developed a short interview for female participants; this interview will help us determine which female participants must have a urine pregnancy test, and when the test should be done. Female participants of childbearing potential who are not pregnant must agree to use appropriate

contraception during the course of the study, and to notify study staff if they become pregnant during the study.

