After the one-week training period, participants will be compensated for CO readings suggesting abstinence and wearing the step-tracker, and will be rewarded a bonus for abstinent CO readings + reaching step goals established by the counselor. Because reinforcers are most effective when delivered immediately after the target behavior is performed (Lattal, 2010), the phone app is designed to allow therapists to provide quick feedback on abstinence status, financial amount earned, and how the amount was calculated.

In order to verify smoking abstinence, participants will use the smart phone app to provide video recordings of him/herself taking CO readings. For each video recording, participants will be asked to 1) begin a recording using the smartphone device; 2) breathe in and hold his/her breath for the duration of the countdown shown on the screen; 3) when prompted, expel all air from lungs into the CO monitor while being video-recorded; 4) hit submit to upload the encrypted video recording using encrypted network connections to the secure server.

Through the smart-phone app, participants log-in to a secure website to upload their video recordings and see personalized information regarding their reinforcement information. Study coordinators can monitor validity and compliance on a daily basis and offer feedback to ongoing

participants regarding compensation so they are well-practiced at the procedures by the time contingent reinforcement is initiated. During the practice week, participants will be compensated \$1 (twice per day) for a valid smoking reading. After the practice week, monetary reinforcement becomes contingent on abstinence, operationally defined as CO readings that are < 6 ppm (after the first week). In the first week of abstinence, smoking cessation compensation will be based not on CO < 6ppm, but on a proportion of participant's baseline CO as defined by Lamb (Lamb, Morral, Kirby, Iguchi, & Galicka, 2004). Because an escalating, versus a fixed reinforcement schedule has produced higher abstinence rates (Heil et al., 2008; Stoops et al., 2009), an escalating schedule will be used in this protocol.

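### Seven-day abstinence at the post-treatment visit is a secondary outcome with no planned biochemical check, so over-reporting there could not be detected on Table 1 timing

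*Combined protocol and SAP*

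**What the plan says.** The Background gives the aim: "The purpose of this pilot project is to evaluate the feasibility, acceptability, and efficacy of STEP UP". On size, Participants says: "We plan to enroll 15 participants in order to reach a goal of 10 study completers".

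**Outcome definition.** Under Outcome Measurement and Biochemical Verification, "Secondary smoking outcomes will include 7- and 30-day point prevalence abstinence at each assessment". Each measure rests only on whether any tobacco was used over its look-back of one week or 30 days. Smoking-Cessation Outcome Measures and Biochemical Verification says the same. This definition has no laboratory criterion. In both sections verification is attached to prolonged abstinence, the primary endpoint at 3 and 6 months.

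**Schedule.** Table 2 marks a 7-day abstinence row weekly, at post-treatment, and at 3 and 6 months. The 30-day row is marked at 3 and 6 months only. Both rows are labelled as prolonged abstinence; I read them as the point-prevalence items because no other row collects these.

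**Sampling.** Table 1 lists Session 8 as a phone contact: "Questionnaires; equipment return; treatment adherence measures". Post-Treatment Session and 3-Month and 6-Month Follow-Up also describes a telephone survey and mentions no sample. For the later visits it says: "If participants report smoking abstinence at the 3 and 6-month follow-ups, they will be asked to come to the laboratory". Saliva and a CO reading are taken there, with mailed saliva as the fallback. During active mobile contingency management (mCM), CO is read on video and abstinence is "operationally defined as CO readings that are < 6 ppm (after the first week". The videos continue through a one-week fading period, when they are paid whatever the reading.

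**Analysis.** Data Analyses plans plots of the longitudinal outcomes to "understand their general trends over time (i.e., post-treatment, 3- and 6-month follow-ups". The sentence does not name abstinence.

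**The concern.** Post-treatment is the scheduled assessment visit nearest the end of mCM, and participants report their smoking aloud to study staff shortly after a period of payment for abstinent readings. If some reports are wrong, nothing planned at that visit would show it. At 3 and 6 months a report of abstinence triggers a request for samples.

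At stake is the credibility of the post-treatment abstinence rate in a pilot meant to inform a larger trial. With so few participants, a single wrong report changes that rate visibly, and a reader of the results would not know that the visits differ in whether a report can be checked.

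**Working it through.** **1. Is a sample planned at Session 8?** Neither Table 1 nor the visit description lists one. The one counter-reading is that the outcome sections collect samples at every follow-up from those reporting prolonged abstinence, and Table 1 uses the word follow-up for Session 8. The payment schedule tests this. From Participant Reimbursement:

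- screening 100 + mCM 798 + equipment 50 + assessments 2 × 25 + saliva 2 × 50 = 1098, the plan's stated total in dollars;
- with a third paid saliva sample: 100 + 798 + 50 + 2 × 25 + 3 × 50 = 1148, which does not match.

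The total fits saliva at 3 and 6 months only, in line with the visit descriptions.

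**2. Do the existing CO videos cover the 7-day window?** From the Table 1 intervals, in weeks after the quit date (Session 4): Session 5 at 1, Session 6 at 2, Session 7 at 2 + 2 = 4 (end of active mCM), end of fading at 4 + 1 = 5. CO videos therefore run to week 5.

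| Reading of Session 8 timing | Visit week | 7-day window (weeks) | Overlap with videos |
|---|---|---|---|
| Table 1, two weeks after active mCM | 4 + 2 = 6 | 5 to 6 | 0 days |
| Table 1, two weeks after fading | 5 + 2 = 7 | 6 to 7 | 0 days |
| Post-Treatment Session text, when mobile assessment closes | 5 | 4 to 5 | 7 days |

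Either way of counting Table 1 leaves the window unobserved. On the text's timing the fading-week videos cover it fully, but no section assigns them to check the outcome.

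**3. Is the equipment available?** Table 1 places equipment return at Session 8. Mobile CM Procedures has the phone and tracker returned once treatment ends, and Protection Against Risk and Data Security Measures has phones retrieved when monitoring ends. The participant keeps the CO monitor, but it reads through the phone (Study Devices). A reading at Session 8 is therefore possible only if the phone has not yet gone back, and the documents differ on that.

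**4. Size.** Change in the rate per false report = 1/n.

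- n = 15: 1/15 = 6.7 points.
- n = 10: 1/10 = 10 points.

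Anything larger needs inputs the documents do not give. As an illustration, assume 40% to 60% report abstinence and 0% to 30% of those reports are false. The overstatement is reporting share × false share: from 0 (no false reports) to 0.60 × 0.30 = 18 points.

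**The case against.** The strongest reply is that point prevalence is defined by tobacco use alone at every visit, so the series is self-report throughout. This stands. A reader might infer that the plan draws a trend from an unverified first point to verified later points. It does not specify one: verification belongs to prolonged abstinence, and the plotting sentence is generic.

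A reader might also infer that a fall from post-treatment to 3 months would be partly false relapse. The documents do not establish that direction. At 3 and 6 months saliva is requested only after a report of abstinence, and $50 is paid for giving the sample, not for a negative result. That could raise abstinence claims at follow-up. At Session 8 the $50 is for equipment return, whatever the smoking status.

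Nor is post-treatment the only evidence on short-term abstinence. Table 2 also collects the 7-day item weekly, alongside CO videos during mCM. And the timing in the visit text would place the post-treatment window inside the video period. Table 2 marks step-tracker data at post-treatment, and remote step monitoring ends one week after treatment, which also fits a visit close to monitoring.

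These points limit what can be claimed, but they leave the gap open. No planned sample or assigned reading checks the post-treatment report, and on Table 1 timing none of the planned data could.

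**Conclusion.** The point holds in a limited form. Seven-day abstinence at post-treatment is a secondary outcome without a planned biochemical check, and on Table 1 timing over-reporting there is undetectable. The size the documents support is 6.7 points per false report with 15 participants, or 10 points with 10. The 0 to 18 point range is an assumption and includes zero.

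The documents do not support saying that the post-treatment rate is inflated, that a later fall would be false, or that the participant certainly still holds the phone. The point concerns only the 7-day measure, because Table 2 has no 30-day item at post-treatment. That absence itself needs reconciling with the statement that both measures are taken at each assessment. The impact is confined to a secondary, descriptive outcome in a small pilot. The change is worth making because it is cheap.

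**What to change.** 1. Reconcile the timing of Session 8 between Table 1 and Post-Treatment Session and 3-Month and 6-Month Follow-Up. Reconcile phone return between Table 1, Mobile CM Procedures and Protection Against Risk and Data Security Measures.
2. If the visit falls when the mobile phase closes, state that the fading-week CO videos will be used to check post-treatment 7-day reports against the trial's own limit of below 6 ppm. If it falls later, add to Session 8 one CO video through the existing app for those reporting 7-day abstinence, uploaded before the phone is returned.
3. In Data Analyses, report self-reported and biochemically checked point prevalence as separate series at post-treatment, 3 and 6 months. State the method of checking at each visit, including whether the 3- and 6-month samples apply to point prevalence.

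CO suits this visit better than cotinine. Nicotine replacement starts at the quit date with an 8-week course of rescue products, so it may still be in use 5 to 7 weeks after quitting, and cotinine is a nicotine metabolite.

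**Cost.** A few sentences of text. Using the fading-week videos needs no new collection. The alternative costs one more reading on a monitor whose number of tests is finite, plus staff review, and some participants will not upload. CO reflects only recent smoking, so it supports but does not prove a 7-day report, and it does not equal the cotinine check at follow-up. That is why the method should be stated visit by visit.
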